The DVD process interview will assess receipt of, viewing of, and satisfaction with the DVD and will be done approximately 2 weeks post-mailing of the DVD. Receipt, experience and satisfaction with the PN intervention, for those randomized to the DVD+PN group, will be assessed as part of the 6 month interview (T2). The 6 month interview will also assess changes in knowledge, patient activation, CRC fear, cancer fatalism, and colonoscopy-related procedural anxiety. Health beliefs for colonoscopy and FIT will be assessed as will self-reported CRC screening intention, uptake and satisfaction with the screening experience (for those who completed screening). At 9 months, we will assess self-reported CRC screening intention, uptake and satisfaction with the screening experience (for those who completed screening since T2). Participants will receive a \$50 gift card for the baseline interview, a \$50 gift card for the 6 month interview and a \$50 gift for completing the 9 month interview; a total of \$150 for participants who complete all three interviews. Participants who complete the additional DVD process interview will receive another \$50 gift card for a total of \$200 in gift cards. By using gift cards with an appealing dollar amount over the 9 month data collection period, we hope to incentivize participants to remain in the study. Additional retention strategies which we will use include mailing

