**C.13. Data Analyses. (IR-3, IR-5, MD-3, MD-5, HT-1, HT-2, HT-3, HT-4)** Preliminary analyses will compare baseline demographic information across groups using means and standard deviations for continuous variables and frequency distributions for categorical variables. We will adjust for those characteristics in subsequent analyses if significant differences emerge at a conservative level for inclusion of a covariate ( $p < .20$ ). Characteristics of participants who drop out by 9 months will be compared with those who remain to determine what biases may exist. **(MD-4)** The above analyses will be conducted using ANOVA, chi-square tests, or exact or non-parametric equivalents. If there appear to be biases in dropout, we will conduct pattern mixture models analyses to see how the results could change based on the MAR assumption **(IR-5, MD-2, MD-3, MD-5)**. Primary analysis of outcomes will employ an intent-to-treat analysis; all participants will be included regardless of compliance with interventions. The main outcome, CRC screening completion with any test (FIT or colonoscopy) will be extracted from medical records for all participants, including those who drop out or are lost to follow-up. Intervention exposure will be measured and its effects will be accounted for in the intent-to-treat analysis. First, we will know whether participants viewed none, part, or all of the DVD. Second, we will document how many contacts PNs make to or on behalf of participants assigned to that group. These variables (viewed none/part/ or all of the DVD and number of navigator contacts) will be added as covariates in analyses. For all aims, sensitivity analysis will be conducted as needed for each outcome to assess the effects of the model assumptions on the results **(IR-5)**. Assumptions, such as normality of residuals, will be checked and appropriate modifications to the analysis plan applied if needed, such as transformations or use of non-parametric methods. From our prior studies, we expect missing data to be minimal (less than 2%) for subjects during participation. For missing data on scales, we will use mean imputation as long as two-thirds of the questions have been answered (or per validated instrument instructions, if otherwise). **(MD-2, MD-3)**

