For Aim 1, we will test the primary hypothesis related to comparing intervention effects among the three randomized groups (H1.1: PN+DVD vs. DVD only and H1.2: PN+DVD vs. usual care and DVD only vs. usual care) using the outcome of completion of CRC screening using any test at 12 months post-baseline. In addition, quality of bowel preparation, procedural anxiety, and satisfaction with the screening experience will be examined as outcomes. As an initial assessment of CRC screening completion at 12 months, we will use a chi-square test for a 3 x 2 (group by screening completion) contingency table to test whether completion rates differ across groups. If the  $p$ -value for the overall test is significant at the .05 level, pair-wise 2 x 2 tests will be conducted at the  $.05/3 = .017$  level. However, the primary analyses for Aim 1 will involve fitting multivariable logistic regression models of the primary outcome of 12-month CRC screening test completion (yes/no). Independent variables will be group assignment and continuous and categorical individual characteristics. These models will also allow us to investigate intervention effects on CRC screening test completion while adjusting for potential confounders. Group assignment will be coded using dummy variables with usual care as the reference category. For H1.3, quality of bowel preparation will be analyzed for those participants who complete colonoscopy with proportional-odds ordinal logistic regression using an ordinal dependent variable ( $1 = \text{excellent}$ ,  $2 = \text{good}$ ,  $3 = \text{fair}$ ,  $4 = \text{poor}$ ,  $5 = \text{inadequate}$ ). If some outcome categories are sparse, the outcome will be dichotomized into adequate

(*excellent or good*) versus inadequate (*fair, poor, or inadequate*). The outcomes of anxiety and satisfaction are continuous outcomes and will be modeled with linear regression.

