## E. Patient Population (RQ-2, RQ-3, RQ-4, PC-1, PC-2)

**E.1. Sample and eligibility criteria.** 450 people who canceled or did not attend their colonoscopy appointment will be enrolled in this study. Participants will be eligible if they are 50-75 years old if non-African American or 45-75 years old if African American and were referred to Eskenazi's endoscopy unit for a colonoscopy. Stratified block random assignment to each of three groups will be performed within 12 strata formed by crossing sex, three race/ethnicity groups, and two age levels (male/female, Black/White/Hispanic, age<65/age 65+) to ensure that the three randomized groups are comparable in distribution of sex, race/ethnicity, and age. At the completion of the baseline interview, patients will be randomly assigned to the tailored DVD-only group, the tailored DVD plus patient navigator group, or usual care. Based on the 65% participation rate we achieved in our recent R01 conducted in this same health system, we conservatively estimated our participation rate at 55%. However, our actual, cumulative participation rate for eligible subjects was 75% through May 31, 2019. Therefore, we will need to contact approximately 600 eligible people to enroll 450. Data from 2014

indicate the availability of 1150 potentially eligible patients during that 12 month period (See Table 6). An estimated 2200 would be available over the 24 month enrollment period. Based on our preliminary studies, no more than 20% attrition was anticipated at 9 months. Actual data from Year 3 of this project as of May 31, 2019 shows an attrition rate closer to 25% at the 6 month follow-up timepoint. This approximate 25% rate is being used in re-calculating the sample size required.

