**Table 6. Colonoscopy orders, completion rates and non-completion rates by race/ethnicity and gender**

Race/ethnicity	Colonoscopies ordered		Colonoscopies completed		Colonoscopies NOT completed	
	N	%	N	%	N	%
Black/African American	1254	64%	505	40.3%	749	59.7%
White/Caucasian	664	34%	280	42.2%	384	57.8%
Hispanic	44	2%	26	59.1%	18	40.9%
Sex: Male	806	41%	324	40.2%	482	59.8%
Female	1156	59%	487	42.1%	669	57.9%
Total	1962	100%	811	41.3%	1151	58.7%

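### Baseline covariates are picked by chance imbalance (p < .20), a rule that almost never selects the randomisation strata and cannot reach baseline anxiety; no fixed baseline list is named

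*Combined protocol and SAP*

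**What the plan says.** Section C.13 (Data Analyses) opens with a comparison of demographic information across the arms and continues: "We will adjust for those characteristics in subsequent analyses if significant differences emerge at a conservative level for inclusion of a covariate", the level being p < .20. This is the only stated rule for choosing baseline covariates.

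The Aim 1 part of C.13 makes multivariable logistic regression the primary analysis. On its content it says: "Independent variables will be group assignment and continuous and categorical individual characteristics". None is named. For the anxiety hypothesis it says: "The outcomes of anxiety and satisfaction are continuous outcomes and will be modeled with linear regression". No baseline term is mentioned, although section C.8 and Table 3 show that procedural anxiety is measured at T1. Section C.8 adds: "The 6 month interview will also assess changes in knowledge, patient activation, CRC fear, cancer fatalism, and colonoscopy-related procedural anxiety". That leaves open whether baseline enters as a covariate, through a change score, or not at all.

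Section E.1 fixes the allocation: "Stratified block random assignment to each of three groups will be performed within 12 strata formed by crossing sex, three race/ethnicity groups", the third factor being age below 65 against 65 and over.

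The only covariates C.13 adds without condition are measures of exposure: "These variables (viewed none/part/ or all of the DVD and number of navigator contacts) will be added as covariates in analyses". Section C.12 expects covariates in the logistic model to raise power above that of the unadjusted comparison.

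**The concern.** Under randomisation, any baseline difference between arms is due to chance. A p < .20 screen therefore finds the variables that happened to be unbalanced, whether or not they predict screening. The strata that the design treats as important are balanced by construction, so the screen passes over them. The power gain expected in C.12 needs prognostic covariates, which the screen does not look for. Because the Aim 1 wording is also open, the content of the primary model is settled only after data are in hand.

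Anxiety is a separate gap. It is not among the demographic items in C.9, so the rule cannot select it, yet the baseline value of a continuous outcome is usually its best predictor.

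Finally, without a list restricted to baseline variables, nothing keeps the two exposure measures out of the intention-to-treat model. Both arise after randomisation, and navigator contacts are zero by design outside one arm.

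**Working it through.** **1. The plan's own figure.** Table 4 gives 92%, 99% and 80% power for 44% v 20%, 44% v 5% and 20% v 5%, at 115 per arm and two-sided .017. The pooled two-proportion formula with continuity correction gives 92.2%, >99.9% and 81.0%; without correction, 94.2%, >99.9% and 86.0%. The stated power therefore comes from tests without covariates.

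**2. How often the rule selects each variable.** Inputs: 450 patients; 12 strata (E.1); shares from the non-completers in Table 6 (482/1151 male; 749 Black, 384 White, 18 Hispanic). Assumed, because not given: block size 3, 6 or 9, and 10-30% aged 65 or over. Stratified permuted blocks were simulated, with a three-arm chi-square test or ANOVA at p < .20 and 6,000 trials per setting.

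| Variable | Selected |
|---|---|
| Sex | 0% |
| Age <65 / 65+ | 0% |
| Race/ethnicity, three levels | 0-1.5% |
| Age as continuous | 1-7% |
| Any unstratified variable | 19-21% |

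A separate simulation with blocks of 3 to 12 and 10-35% aged 65 or over gave 0%, 0%, 0-1.2%, 0.8-6.7% and about 20%.

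**3. Chance entries.** C.9 lists six demographics unrelated to the strata: marital status, household size, education, employment, income and insurance. Expected entries are 6 × 0.2 = 1.2. The chance of at least one is 1 − 0.8^6 = 0.74 if they are independent, and 0.61 in simulation at an assumed pairwise correlation of 0.5.

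**4. How prognostic the strata are.** From Table 6, log odds ratios of completion with Woolf intervals:
- female v male: ln[(487/669)/(324/482)] = 0.08 (−0.10 to 0.26)
- White v Black: ln[(280/384)/(505/749)] = 0.08 (−0.11 to 0.27)
- Hispanic v Black: ln[(26/18)/(505/749)] = 0.76 (0.15 to 1.37), in about 2% of patients

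These describe completion among all orders, not later screening of non-attenders, and Table 6 says nothing on age.

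**5. Effect on the primary outcome.** The outcome is "extracted from medical records for all participants, including those who drop out or are lost to follow-up", so 150 per arm applies. With rates of 5/20/44%, the log odds ratios above and likelihood-ratio tests at .05/3 (20,000 trials per setting), unadjusted power is 95.8-96.3% for 20% v 5% and 98.3-98.6% for 44% v 20%. Adding sex, race (Hispanic pooled) and age group gains:
- 0.02-0.06 points at an assumed age log odds ratio of 0-0.08
- about 0.1 points at 0.5
- 0.2-0.3 points at 1.0

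The Monte Carlo standard error of these gains is 0.02-0.04 points. Under the null at nominal 5%, rejection is 4.5-5.2% unadjusted and 5.1-5.4% adjusted.

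**6. Effect on anxiety.** With baseline-to-follow-up correlation r, the residual variance is 1 − r² when baseline is a covariate, 1 when it is ignored, and 2(1 − r) for a change score. The saving in patients is 1/(1 − r²) − 1 against ignoring baseline and 2/(1 + r) − 1 against a change score. The documents give no r, so a range is assumed.

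| r | v ignoring baseline | v change score |
|---|---|---|
| .3 | 1/0.91 − 1 = 10% | 2/1.3 − 1 = 54% |
| .5 | 1/0.75 − 1 = 33% | 2/1.5 − 1 = 33% |
| .7 | 1/0.51 − 1 = 96% | 2/1.7 − 1 = 18% |

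Hypothesis 1.3 concerns colonoscopy completers only. If every test were a colonoscopy there would be at most 8/30/66 of them (5/20/44% of 150). Simulated savings are then 8-9%, 32-33% and 93-95% against ignoring baseline, or 51-55%, 31-32% and 15-16% against a change score. With an assumed 2/8/17 completers they are about 5%, 27-28% and 86-90%, or 46%, 27% and 11-13%. At r = 0, adjustment loses 1-4% against ignoring baseline.

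**7. Exposure terms, illustration only.** Assumed: exposure unrelated to outcome; 8-30% view none of the DVD (8% from the 92% viewing in the mailed-DVD trial in B.1) and 10-30% view part; at least two contacts per navigated patient, with Poisson or negative binomial excess. Wald tests at .05/3, 150 per arm, 2,500 trials per setting. Adding both terms cuts power from about 95% to 54-87% (DVD v usual care) and from about 98% to 36-83% (PN+DVD v DVD).

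**The case against.** The strongest reply is that little is lost on the primary outcome. That is right, and step 5 says so. The initial chi-square tests use no covariates and are untouched, although C.13 calls the multivariable models the primary analyses.

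A second reply tests the p < .20 rule directly against a strata-only list, with six unstratified standardised demographics of assumed prognostic strength. Power for DVD v usual care / PN+DVD v DVD was:

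| Log odds ratio of each demographic | p < .20 rule | Strata list |
|---|---|---|
| 0 | 96.1 / 98.4 | 96.1 / 98.7 |
| 0.2 | 96.4 / 97.2 | 96.2 / 97.0 |
| 0.4 | 96.1 / 94.7 | 95.5 / 93.8 |

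Null rejection under the rule was 3.6-5.4%, so it does not inflate error. This stands as a limit on the size of the point. But the rule's edge needs six strongly prognostic demographics, and in that case fixing all six does better than either (97.5 / 96.9). It argues for choosing the list well, not for choosing it by imbalance.

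Third, the wording may already allow the strata: individual characteristics are left open, and the Aim 2 models are built on those of Aim 1 by adding interactions with age, race/ethnicity, sex and income. That reading is possible, but nothing commits Aim 1 to it.

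Fourth, the anxiety gain rests on an assumed correlation and the exposure figures on assumed distributions. Both are true. The exposure sentence also has to be dealt with in its own right, since removing the p < .20 rule would leave it in place.

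**Conclusion.** The plan should be changed on this point. The rule selects on chance imbalance, almost never selects the stratification factors, does not reach baseline anxiety, and is not backed by any fixed list.

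For the primary binary outcome the consequence is small: 0.02 to 0.3 points of power, and at most a slightly conservative test if the strata are left out. For anxiety the gain is larger, but it depends on the unknown correlation and runs from a loss of 1-4% at r = 0 to a saving of 96% at r = .7. The near-zero selection of sex and age band held across every block size and age mix tried. The fall in power from the exposure terms is illustrative. What does not depend on the assumed distributions is that, once post-randomisation exposure is in the model, the arm coefficient no longer estimates the intention-to-treat contrast.

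**What to change.** In C.13, replace the p < .20 rule with a fixed list of baseline covariates, set before outcome data are examined:

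- Sex, race/ethnicity and age group in every Aim 1 model. Pool the Hispanic level (450 × 18/1151 ≈ 7 patients expected) and state with which group.
- The T1 State Anxiety score as a covariate in the anxiety model.
- Any other demographic thought to be prognostic, such as education, income or insurance, named now and not left to a test of imbalance.
- A reduced list, written out, for the small completer-only models.

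Keep the comparison of arms at baseline as a descriptive table. State that the list holds baseline variables only, and amend the exposure sentence so that DVD viewing and navigator contacts are reported in a separate, labelled exposure analysis outside the primary intention-to-treat model.

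The cost is SAP wording; every variable is already collected.

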- *Missing data:* Missing data will be minimized through the use of telephone data collection methods and through interviewer training. All characteristics at baseline will be examined to determine potential bias that would require subsequent caution regarding interpretation of results.
- *Limited generalizability:* We will recruit participants from one safety net system who will be predominantly low-income, which limits generalizability. However, we will compare outcomes for a racially diverse group of low-income patients and explore whether age, sex, or race/ethnicity moderate the effects of the two interventions. (*RQ-4, IR-6*)
- *Sample bias:* Based on our preliminary studies, we estimate that approximately 55% of eligible people who are contacted will be willing to participate. It is possible that those who are motivated to complete CRC screening will self-select into the study. To examine the representativeness of our sample, we will compare demographic characteristics of those who agree to participate with those who do not. (*PC-2, IR-6*)

**C.15. Impact:** At the completion of this study, we will have developed two theory-based and highly translatable and easy to disseminate interventions to promote CRC screening and improve quality of bowel preparation for those who undergo colonoscopy. These interventions will be designed to be flexible and modifiable as science advances and as the needs of individual patients and health care systems change. Interventions that are easily modified to meet the needs of diverse populations and settings that counsel patients about the need for CRC screening, support them to complete screening in a timely manner, and assist those who undergo colonoscopy to properly prepare (cleanse their bowel) for the procedure are urgently needed. Knowledge of the comparative effectiveness of these interventions will inform the next steps required for translation of interventions into clinical practice.

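### C.13 runs its pattern-mixture analysis only if dropouts and stayers look different, which cannot show whether interview results need a test of departures from MAR

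*Combined protocol and SAP*

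**What the plan says.** Section C.13 (Data Analyses) sets up the check: "Characteristics of participants who drop out by 9 months will be compared with those who remain to determine what biases may exist". The tests are named ("The above analyses will be conducted using ANOVA, chi-square tests, or exact or non-parametric equivalents"), but no significance level is given for this use. What follows is conditional: "If there appear to be biases in dropout, we will conduct pattern mixture models analyses to see how the results could change". The sentence ends by referring to the MAR assumption and specifies no departure from it.

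Section C.14, under missing data, adds: "All characteristics at baseline will be examined to determine potential bias that would require subsequent caution regarding interpretation of results". C.13 also has a general provision for all aims: "sensitivity analysis will be conducted as needed for each outcome to assess the effects of the model assumptions on the results".

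The main outcome is protected. Screening completion "will be extracted from medical records for all participants, including those who drop out or are lost to follow-up".

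Table 3 collects knowledge and health beliefs at baseline and 6 months (T2) only. Procedural anxiety is collected at baseline, T2 and 9 months (T3), and satisfaction with screening at T2 and T3. C.9 lists anxiety and satisfaction among the primary outcomes. C.13 models both by linear regression and states no method for a missed interview. On the amount of loss, E.1 reports that project data "shows an attrition rate closer to 25% at the 6 month follow-up timepoint", and C.14 expects about the same over 9 months.

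**The concern.** A pattern-mixture analysis asks what happens if people who were not interviewed differ on the outcome from similar people who were. Observed characteristics do not answer that. Where dropouts differ on something measured, adjustment can deal with it. Where they differ on the part of the outcome that the measured variables do not explain, the check has nothing to see. The plan therefore makes the analysis depend on evidence that cannot bear on the need for it.

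The definition of dropout adds a second fault. C.8 provides a letter telling participants who miss the 6-month interview that they may stay in the study. Someone who misses T2 and returns at T3 is a stayer by the 9-month rule, yet has no change score for any Aim 3 mediator.

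At stake are the mediation results, and the anxiety and satisfaction comparisons among colonoscopy completers. These could be reported with no test of departures from MAR because a check that could not detect the problem had found nothing.

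**Working it through.** **1. Amount missing.** The plan gives no figure for how its trigger performs, so the only figure to reproduce is the attrition. C.12 takes 150 per arm down to 115: 1 − 115/150 = 23.3%, which agrees with its approximate 25%. I use m = 0.25.

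**2. Where the check and the data part.**

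| Result | Interviews after baseline (Table 3) | Captured by dropout by 9 months? |
|---|---|---|
| Aim 3 mediators | T2 only | No, if T2 is missed and T3 is done |
| Procedural anxiety | T2 and T3 | Largely; a T2-misser can still contribute at T3 |
| Satisfaction with screening | T2 and T3, only if screened | Largely |
| Screening by 12 months | None (medical record) | Not relevant |

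**3. Size of a possible bias.** Let δ be the mean outcome of dropouts minus that of stayers within an arm, in SD units. The full-arm mean is (1 − m)S + m(S + δ) = S + mδ, where S is the stayers' mean. Using stayers alone misses mδ in that arm, so an arm contrast is off by m(δ₁ − δ₀) in absolute size. The values of δ are assumptions, because the documents give no outcome data on dropouts.

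| δ | One arm only | Two arms, opposite signs |
|---|---|---|
| 0.2 SD | 0.25 × 0.2 = 0.05 SD | 0.25 × 0.4 = 0.10 SD |
| 0.3 SD | 0.25 × 0.3 = 0.075 SD | 0.25 × 0.6 = 0.15 SD |
| 0.5 SD | 0.25 × 0.5 = 0.125 SD | 0.25 × 1.0 = 0.25 SD |

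If δ is the same in both arms, the contrast does not move.

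**4. Does a comparison of characteristics see it?** I simulated 4000 trials of 150 per arm with 25% dropout in each arm and no true arm effect. There was one baseline covariate, correlated 0.3 with the outcome, and dropout had a log-odds slope of 1 per SD. The trigger was a dropout-versus-stayer t-test on the covariate at .05.

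| Dropout depends on | Trigger fires | Arm-by-dropout test fires | Bias unadjusted | Bias adjusted |
|---|---|---|---|---|
| Nothing | 5.5% | 5.1% | 0.00 SD | 0.00 SD |
| Baseline covariate, opposite directions in two arms | 5.0% | about 100% | −0.125 SD | 0.00 SD |
| Part of outcome unexplained by baseline, one arm | 5.2% | 5.3% | −0.20 SD | −0.20 SD |
| The same, two arms in opposite directions | 4.7% | 5.2% | −0.40 SD | −0.40 SD |

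The last two rows carry the point. Neither check departs from its false-positive rate, and adjustment does not help. The second row does not support the point: an arm-specific check would see that pattern, and baseline adjustment removes its bias.

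**5. Many characteristics.** The 5% is for one covariate at an assumed .05. Ten independent null characteristics would fire the trigger with probability 1 − 0.95^10 = 40%, or 1 − 0.8^10 = 89% at the p<.20 level that C.13 uses for choosing covariates. That firing is chance, unconnected with outcome-related dropout of the kind in the last two rows.

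**6. The H1.3 populations.** H1.3 concerns participants who complete colonoscopy. At the any-test rates assumed in C.12, 150 × 0.44 = 66, 150 × 0.20 = 30 and 150 × 0.05 = 7.5 would be screened by either test. Usual care would thus have at most about 7 or 8 colonoscopy completers. The formula in step 3 still applies, but m among colonoscopy completers is not given and need not be 25%.

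**The case against.** The strongest reply is that the plan is vague here rather than wrong. The C.13 sentence does not confine the comparison to baseline data; that comes from C.14. It does not say that arms are pooled. Arm is a known characteristic, no threshold limits what may appear biased, and the monitoring plan has attrition watched continuously. A reader might infer a check that is blind to arm by design. The documents do not support that, because it rests only on the absence of an arm term.

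A reader might also take the 5% firing rate as that of the planned procedure. It is not: with many characteristics examined, the trigger could fire often by chance (step 5).

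Nor do the documents show that dropout differs by arm. Contact and payment differ by design: C.8 says of the DVD arms "Participants who complete the additional DVD process interview will receive another" gift card, and only DVD plus navigation brings navigator calls. But the interview gift cards, check-in calls and newsletters go to everyone, and no attrition by arm is reported.

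Loss is put at about 25% both at 6 months and over 9 months, so there is no sign that many participants miss T2 and return. The general sensitivity sentence leaves room for further work, so it cannot be said that unadjusted complete-case results will necessarily stand.

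All of this narrows the point without removing it. However the comparison is arranged, it uses observed characteristics, and step 4 shows that an arm-specific version fails in the same way. The general sentence is discretionary and commits to nothing for missed interviews. The expectation in C.13 of under 2% missing data concerns people while they participate, and its mean-imputation rule concerns partly answered scales. Neither covers dropout.

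**Conclusion.** The point holds for interview-based results. A trigger based on observed characteristics cannot decide whether a test of departures from MAR is needed, and dropout by 9 months is the wrong definition for mediators measured at 6 months. The timing fault applies mainly to Aim 3.

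The documents do not fix the size. At 25% missing, the shift in an arm contrast is 0.05 to 0.125 SD if one arm's dropouts differ from its stayers by 0.2 to 0.5 SD, and 0.10 to 0.25 SD if two arms differ in opposite directions. The larger simulated values rest on a steep assumed dropout slope and are illustrations, not forecasts. For H1.3 the fraction missing among colonoscopy completers is unknown.

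It would be wrong to infer that the trial's main conclusion is at risk. Screening by 12 months is taken from records for all participants, and the correction changes no sample size, alpha or power figure. This is a worthwhile, inexpensive improvement to the analysis plan.

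**What to change.** In C.13, replace the conditional sentence with an analysis that is always run:

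1. Define missingness separately for T2 and T3. Report it by arm, with the characteristics of those missing by arm, as description and not as a gate.
2. For each interview outcome and mediator, fit the main model under MAR with baseline predictors of the outcome and of missingness.
3. Always follow with a delta-adjusted pattern-mixture analysis. Shift the missing values by amounts set separately for each arm, for example 0 to 0.5 SD in either direction, including opposite directions in two arms. State the shift at which the conclusion changes.
4. Name the population each time: all randomised participants for the Aim 3 mediators, and colonoscopy completers for H1.3 anxiety and satisfaction. For H1.3, give counts missing by arm, since usual care may have very few.

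The cost is SAP wording and a modest amount of extra analysis. No new data are needed.
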